**Table 4: Schedule of Assessments**

**Note: Upon implementation of Protocol Amendment 4, only the schedules of assessments in Table 6 and Table 7 should be followed.**

Procedure	Section	Screening	Treatment				EOT	Safety Follow-Up	Disease Follow-Up	Survival Follow-Up
		Day -28 to -1	Day 1	Day 15 (± 3 Days)	Every 3 Weeks (± 3 Days)	Every 12 Weeks (± 3 Days)		EOT + 30-35 Days		Every 12 Weeks (± 1 Week)
Informed consent	7.1	X								
Contact IWRS	7.2	X	X		X		X			
Inclusion & exclusion criteria	3.1 3.2	X	X							
Demography and medical history	7.3.1	X								
Prior/concomitant medications	7.3.1.1	X	X	X	X		X	X		
Comprehensive physical exam	7.4.2	X a					X			
Disease-specific physical exam	7.4.2.1		X	X	X			X		
Vital signs	7.4.3	X	X	X	X		X	X		
12-lead ECG	7.4.4	X	X	X		X	X	X		
ECOG status	7.5.6	X	X		X		X	X		
AE assessment	7.4.1	X	X	X	X		X	X		
FDG-PET/CT scan	7.5.1 7.5.2	X	Every 9 weeks (± 1 week) through Week 27, then every 18 weeks (± 1 week) thereafter. b							
Bone marrow exam	7.5.3	X c								
Study drug dispensing	5.1		X		X d					
Study drug accountability	5.3		X		X		X			
INCB050465 administration	5.2.1		X	X	X					
Disease follow-up	6.4.2								X e	
Survival follow-up	6.4.3									X f

FDG = fluorodeoxyglucose; PET = positron emission tomography.

a Height required at screening only.

b If the PET-CT is of diagnostic quality, then a separate CT does not need to be performed. If CT is not available, is not practicable, or is contraindicated, then an MRI may be substituted. Every effort must be made to use the same modality for disease assessment throughout the study for each individual subject.

c Required at baseline except for reasons provided in Section 7.5.3. Also required if needed to confirm CR/CMR.

d Study drug will be dispensed at Weeks 1, 4, 7, and 10, and every 12 weeks thereafter.

e Only for subjects who discontinue study treatment for reasons other than disease progression.

f May be conducted by phone or email.

**Table 5: Schedule of Laboratory Assessments**

**Note: Upon implementation of Protocol Amendment 4, only the schedules of assessments in Table 6 and Table 7 should be followed.**

Laboratory Tests	Section	Screening	Treatment				EOT	Safety Follow-Up
		Day -28 to -1	Day 1	Day 15 (± 3 Days)	Every 3 Weeks (± 3 Days)	Other		EOT + 30-35 Days
Serum chemistries	7.4.5.1	X	X a	X	X		X	X
Hematology	7.4.5.1	X	X a	X	X		X	X
Serology	7.4.5.3	X				X b		
Serum pregnancy	7.4.5.2	X c					X	
Urine pregnancy	7.4.5.2				X d			
HIV testing	7.4.5.4	X e						

a Day 1 tests may be omitted if the screening tests occurred in the preceding 7 days. If needed, Day 1 blood draws should be performed before dose administration.

b Samples for CMV DNA analysis only will be collected every 3 weeks for 10 weeks (Day 1 of Weeks 4, 7, and 10) and then every 12 weeks thereafter.

c Only for female subjects of childbearing potential; negative pregnancy test must be obtained within 14 days before administration of study drug.

d Only for females of childbearing potential.

e Optional for subjects enrolled in the United States.

[REDACTED]

**Table 6: Schedule of Assessments for Ongoing Subjects in All Cohorts Upon Implementation of Protocol Amendment 4**

Procedure	Section	At Least Every 12 Weeks in Clinic a	EOT	Follow-Up		Notes
				EOT + 30-35 Days		
Prior/concomitant medications	7.3.1.1	X	X	X		Review to ensure no prohibited medications are being used. Provide data to sponsor in regard to SAEs only.
Study drug dispensing	5.1	X				
Study drug accountability	5.3	X	X			
Distribute reminders	7.8.2	X	X			
Laboratory tests	Table 7	X	X	X		Performed at each site as per standard of care and monitored per investigator discretion.
AEs/SAEs	7.4.1	X	X	X		AEs that lead to the discontinuation of study treatment and all SAEs must be recorded in the CRFs, regardless of the causal relationship.
FDG-PET/CT scan	7.5.1 7.5.2					Performed per standard-of-care guidelines.

a Information related to concomitant medications and adverse events may also be collected between the required clinic visits (eg, by phone or email).

**Table 7: Schedule of Laboratory Assessments for Ongoing Subjects in All Cohorts Upon Implementation of Protocol Amendment 4**

Local Laboratory Tests	Section	At Least Every 12 Weeks in Clinic	EOT	Follow-Up		Details
				EOT + 30-35 Days		
Serum chemistries	N/A	X	X	X		Performed at each site as per standard of care and monitored per investigator discretion.
Hematology	N/A	X	X	X		Performed at each site as per standard of care and monitored per investigator discretion.

**Table 8: Laboratory Tests: Required Analytes (Not Applicable After Implementation of Protocol Amendment 4)**

Serum Chemistries	Hematology	Serology	Other
Albumin	Hemoglobin	HBsAg	Pregnancy Test Female subjects of childbearing potential require serum pregnancy and urine pregnancy tests (see Table 5).
Alkaline Phosphatase	Hematocrit	Anti-HBsAg	
ALT	Platelet count (absolute)	Anti-HB core IgG	
AST	Red blood cell count	HCV antibody	
Bicarbonate	White blood cell count	HCV-RNA	
Blood urea nitrogen	Differential cell count:	HBV-DNA	
C-reactive protein	Basophils %	CMV DNA	
Calcium	Eosinophils %	HIV antibody b (immunoassay)	
Chloride	Lymphocytes (absolute)		
Creatinine	Monocytes		
Glucose	Neutrophils (absolute)		
Lactate dehydrogenase			
Phosphate			
Potassium			
Sodium			
Total bilirubin			
Direct bilirubin a			
Indirect bilirubin a			
Total serum protein			
Total cholesterol			

Note: Additional laboratory tests may be required, as agreed by investigator and sponsor, based on emerging safety data.

a Only required if total bilirubin is > ULN.

b Optional for subjects enrolled in the United States.

### 6.1. Screening

Screening is the interval between signing the ICF and the date that the study treatment is first administered (Day 1). Screening may not exceed 28 days. Assessments that are required to demonstrate eligibility may be performed over the course of 1 or more days during the screening process. Central laboratory results for serum chemistry, hematology, serology, and serum pregnancy will be used to determine eligibility.

Procedures conducted as part of the subject's routine clinical management (eg, imaging study) and obtained before signing of informed consent may be used for screening or baseline purposes, provided that the procedure meets the Protocol-defined criteria and has been performed in the screening interval. All information associated with eligibility requirements must be entered into the appropriate eCRF pages.

Results from the screening visit evaluations will be reviewed by the investigator to confirm subject eligibility before enrollment or the administration of study drug. Tests with results that fail eligibility requirements may be repeated during screening if the investigator believes the results to be in error. For screening assessments that are repeated, the most recent available result before administration of study drug will be used to determine subject eligibility. Additionally, a subject who fails screening may repeat the screening process 1 time if the

investigator believes there has been a change in eligibility status (eg, after recovery from an infection). Such subjects will be assigned a new subject ID number.

## **6.2. Treatment**

The treatment period begins on the day that the subject receives the first dose of study drug (Day 1). This day must be no more than 28 days after the subject has signed the ICF. Dates for subsequent study visits will be determined based on this day and should occur within the visit windows outlined in the schedule of assessments (see [Table 4](#)) unless delayed for safety reasons. Subjects may receive treatment until disease progression, death, unacceptable toxicity, or consent withdrawal.

## **6.3. End of Treatment**

There is no predefined EOT. If a subject permanently discontinues study treatment, then the EOT visit should be conducted. The subject should be encouraged to return for the safety follow-up visit.

## **6.4. Follow-Up**

### **6.4.1. Safety Follow-Up**

The safety follow-up period is the interval between the EOT visit and the scheduled follow-up visit, which should occur 30 to 35 days after the EOT visit (or after the last dose of study drug if the EOT visit was not performed). Adverse events and SAEs must be reported up until at least 30 days after the last dose of study drug, the date of the follow-up visit, or until toxicities resolve, return to baseline, or are deemed irreversible, whichever is longer. Reasonable effort should be made to have the subject return for the follow-up visit and report any AEs that may occur during this phase.

If a subject is scheduled to begin a new anticancer therapy before the end of the safety follow-up period, then the safety follow-up visit should be performed before new anticancer therapy is started. Once new anticancer therapy has been initiated, the subject will move into the survival follow-up period.

### **6.4.2. Disease Status Follow-Up**

Subjects who discontinue study treatment for a reason other than disease progression will continue to be followed for disease assessments by radiologic imaging per the schedule of assessments (see [Table 4](#)). Every effort should be made to collect information regarding disease status until any 1 of the following occurs:

- The start of new antineoplastic therapy.
- Disease progression.
- Death.
- The end of the study.

### **6.4.3. Survival Follow-Up**

Once a subject has received the last dose of study drug, confirmed disease progression, or started a new anticancer therapy, the subject moves into the survival follow-up period. The site will use continuing subject records to supply data on subsequent treatment regimens, tumor assessments (if discontinued treatment for a reason other than progression), and OS in the eCRF.

For subjects who do not intend to return to the study investigator for their ongoing care, follow-up should be maintained to assess for survival status until death, withdrawal of consent, or the end of the study, whichever occurs first.

### **6.5. End of Study**

The study will continue up to 2 years after the first dose of study treatment is administered to the last subject enrolled, at which point the study will be closed.

### **6.6. Unscheduled Visits**

Unscheduled visits may be held at any time at the investigator's discretion, and appropriate clinical and laboratory measurements performed based on AEs or other findings.

## **7. CONDUCT OF STUDY ASSESSMENTS AND PROCEDURES**

Subjects ongoing after implementation of Protocol Amendment 4 will only have assessments performed as indicated in [Table 6](#) and [Table 7](#) and at a frequency determined by the investigator as guided by the standard of care. **Unless noted below, procedures listed in this section are not required to be performed or collected in the CRF after implementation of Amendment 4.**

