
Study Schedule/Procedures: During screening and every 21 days from the date of first study drug administration (Day 1), a study visit will be conducted that includes a physical examination, clinical laboratory tests, and an assessment of AEs. [REDACTED]
 
[REDACTED]
 
During screening, subjects will have an objective assessment of disease status performed by fluorodeoxyglucose (FDG) positron emission tomography (PET) and diagnostic quality CT scan or MRI. Subjects will also have a bone marrow biopsy performed at screening unless the subject has FDG-avid disease or has undergone a recent bone marrow biopsy. Disease status will be subsequently assessed by PET-CT/MRI at Weeks 9, 18, 27, and every 18 weeks thereafter until disease progression. On-study bone marrow biopsies will be required only if needed to confirm a CR/CMR.
 
Subjects withdrawn from study treatment for reasons other than disease progression will be followed for disease assessment until either radiologic disease progression, the start of a new anticancer therapy, or death (whichever occurs first).
 
Subjects withdrawn from study treatment because of disease progression will be followed approximately every 12 weeks for subsequent anticancer therapies and survival.
 
Note: With Amendment 4, Protocol-required procedures have been reduced for ongoing subjects.

Estimated Duration of Participation: Subject participation through safety follow-up is expected to average approximately 11 months, which includes the following:
 

• A screening period lasting up to 28 days.

• A treatment period lasting as long as the subject is receiving benefit, tolerating the regimen, and has not met withdrawal criteria (approximately 9 months).

• A safety follow-up period lasting 30 to 35 days.

 
Subjects will be followed for approximately 12 months after the safety follow-up period.

Estimated Number of Subjects: The target enrollment for this study is 100 to 120 subjects.

Principal Coordinating Investigator: [REDACTED], MD, [REDACTED]

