## 6. STUDY ASSESSMENTS

See the schedule of assessments ([Table 4](#)) and schedule of laboratory assessments ([Table 5](#)) for the timing of all assessments. All assessments mandated throughout the study must be performed on a calendar schedule; delays in treatment administration will not delay performance of assessments. A table of clinical laboratory analytes to be assessed ([Table 8](#)) is provided. The order of assessments is suggested by the order listed within the Schedule of Assessments. See [Sections 6](#) and [7](#) for instructions on each assessment. Further details of study procedures and assessments can be found in the study reference manual.

**Note: Upon implementation of Protocol Amendment 4, only study assessments indicated in [Table 6](#) and [Table 7](#) will be performed.**

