### **7.4. Safety Assessments**

Upon implementation of Amendment 4, only safety assessments (including laboratory analytes) that are consistent with standard of care and monitoring should be performed per the investigator's discretion. Subjects must be taken off study treatment if, in the opinion of the investigator, an unacceptable toxicity develops.

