#### **7.5.1. FDG-PET or Combined PET-CT**

Positron emission tomography using [F] fluorodeoxyglucose (FDG), or combined PET-CT is required to evaluate disease burden during the screening phase. If FDG-PET assessment was performed as standard of care before signing of the ICF but within 28 days of Day 1, the results from that assessment may be recorded in the eCRF in lieu of a study-specific assessment.

Scheduled assessments should always be calculated from the first dose of study treatment. Imaging should not be delayed for delays in treatment.

**Note:** Subjects who discontinue study treatment for any reason other than disease progression or withdrawal of consent will be followed according to the disease assessment schedule until either disease progression, the start of a new anticancer therapy, or death, whichever occurs first.

Upon implementation of Amendment 4, FDG-PET or combined PET-CT assessments are only required to be performed as per standard of care guidelines and monitored. Subjects must be taken off study if, in the opinion of the investigator, the disease has progressed and the subject is no longer having clinical benefit from the study treatment.

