### **7.8.3. Data Collection for Survival Follow-Up**

For subjects having entered the survival follow-up period of the study, the site will collect data as described (see Section 6.4.3).

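### For subjects still on treatment at Amendment 4, the only schedule in force has no survival contact and progressing subjects are to leave the study, while other sections still require survival follow-up for OS

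*Protocol*

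**What the plan says.** Three statements in the protocol limit what is done once Amendment 4 is in force:

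- Section 6: "Upon implementation of Protocol Amendment 4, only study assessments indicated in" Tables 6 and 7 are to be carried out.
- The note on Table 4, the table that holds the 12-weekly survival column: "Upon implementation of Protocol Amendment 4, only the schedules of assessments in Table 6 and Table 7 should be followed".
- Section 7: "Unless noted below, procedures listed in this section are not required to be performed or collected in the CRF after implementation of Amendment 4".

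Table 6 has three contact points: clinic visits at least every 12 weeks, end of treatment (EOT), and 30 to 35 days after EOT. It has no entry for survival status or new anticancer therapy. Its imaging row says only "Performed per standard-of-care guidelines" and points to 7.5.1 and 7.5.2.

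Sections 7.5.1 and 7.5.2 use the same instruction for progression: "taken off study if, in the opinion of the investigator, the disease has progressed and the subject is no longer having clinical benefit". The matching sentence on toxicity in 7.4 is worded differently: "Subjects must be taken off study treatment if, in the opinion of the investigator, an unacceptable toxicity develops".

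Section 7.8.3 begins "For subjects having entered the survival follow-up period of the study, the site will collect data as described" and refers back to 6.4.3. It carries no Amendment 4 sentence, although 7.8.1 and 7.8.2 do.

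Other current text goes the other way. The synopsis (Study Schedule/Procedures) says: "Subjects withdrawn from study treatment because of disease progression will be followed approximately every 12 weeks for subsequent anticancer therapies and survival". Section 4.1 has subjects followed for survival after treatment ends and schedules an OS analysis at closure. Section 5.5 says that stopping treatment does not complete the study. Section 6.4.3 keeps survival status under follow-up until death, consent withdrawal or study end. OS in Group A is a secondary endpoint (2.2.2), and SAP 7.3.3 censors it at the date last known alive.

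**The concern.** A site reading the Amendment 4 text has one schedule, and that schedule runs out at the safety visit. The same site is told to take a progressing subject off study. On that reading survival contact ends about a month after treatment stops, and the subject is censored for OS near that date.

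This censoring is tied to prognosis. Subjects who have just progressed can be expected to have a higher hazard of death than those still at risk, whereas the Kaplan-Meier estimate assumes that censored subjects share the hazard of those who remain. A site that goes by 6.4.3 or the synopsis would keep collecting deaths. The completeness of OS would then depend on how each of about 80 planned sites read the document.

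Safety reporting does not fill the gap. Under 8.3.2, a serious event more than 30 days after the last dose is reported only if the investigator suspects a link to the drug, and Amendment 4 leaves that rule as it was.

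**Working it through.** The plan states no figure on this point, so the check is mainly a comparison of texts.

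**1. Which schedule applies.** Section 6 and the Table 4 note both say only Tables 6 and 7. Table 4 is the only schedule with a survival column, and its footnote f allows contact by phone or email. Once it is set aside, no schedule in force contains a survival contact.

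**2. Whether Table 6 covers only on-treatment visits.** It does not. It continues through EOT to the visit 30 to 35 days later and then stops. The missing survival line therefore falls within the period after treatment, and it affects anyone who stops the drug after the amendment, for progression or toxicity.

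**3. What happens at progression.** Sections 7.5.1 and 7.5.2 say off study; 7.4 says off study treatment. Sections 5.5 and 5.5.2 treat these as different states, since leaving treatment starts follow-up and does not end the study.

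**4. Whether another section settles it.** Section 6.4.3 keeps the duty but gives no contact interval. The interval of about 12 weeks stands only in the synopsis and in Table 4, which is set aside. The general note in the synopsis and 4.1 says that procedures are reduced for ongoing subjects but does not mention survival. The SAP does not help: it remains effective for later amendments (2.1), takes its schedule from Amendment 3 (3.4) and lists one version (Table 4).

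**5. Contacts lost per affected subject.** Inputs: about 12 months of follow-up after the safety period (synopsis) and 12-weekly contacts, or 84 days.

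- 365 / 84 = 4.3, so at most about 4 contacts. Counted from EOT, the first would fall at about day 84, after the last Table 6 contact at day 30 to 35.
- Closure can reduce this. The study closes no later than 2 years after the last subject's first dose, a date the documents do not give. Assume that the estimated 1.5-year accrual ran from Amendment 3 (23 FEB 2017). Last enrolment is then about 23 AUG 2018 and closure about 23 AUG 2020. From Amendment 4 (05 NOV 2019) that is 292 days, and 292 / 84 = 3.5, so at most 3 contacts even for a subject who stops on the amendment date. Four contacts need 4 × 84 = 336 days, that is, a last enrolment in about OCT 2018 or later.

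**6. How many subjects.** The number on treatment at Amendment 4 is not given. If it is *k* of the 100 planned in Group A, at most *k*/100 of the OS outcomes are exposed: 1% for *k* = 1 and 20% for *k* = 20. These values of *k* are assumptions for scale only.

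**7. Where on the curve.** Affected subjects were alive and on treatment when the amendment took effect. Their OS times before that date are intact, so any distortion falls on late follow-up.

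**8. The review committee.** Section 7.5.4 lies in Section 7 and has no Amendment 4 note, so under "Unless noted below, procedures listed in this section are not required to be performed or collected in the CRF after implementation of Amendment 4" sending scans to the independent review committee (IRC) is no longer required. Yet 7.5.4 itself and SAP 7.2.1 still say that all imaging is submitted, and SAP 7.3.1 and 7.3.2 take progression dates from that review.

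**The case against.** The best reply is that survival follow-up was never switched off. The Section 7 rule covers procedures in Section 7, whereas the duty sits in 4.1, 5.5.2 and 6.4.3; Section 7.8.3 only points back to 6.4.3. The stated purpose of Amendment 4 is to lighten procedures for subjects who remain on treatment, Table 6 is titled for ongoing subjects, and 6.4.3 is not listed among the changed sections. Section 6.4.3 also lets sites supply OS data from continuing records, so a missing schedule line need not mean missing data. OS is descriptive, with no hypothesis attached.

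Much of this stands. The Section 7 rule alone does not end survival follow-up, and the off-study wording is probably loose drafting. But the reply does not answer the notes in Section 6 and on Table 4, which limit the whole schedule, or the instruction to take progressing subjects off study. It shows what was probably meant, not what a site is told to do.

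Two stronger readings are tempting. A reader might infer that Amendment 4 ends survival follow-up outright. The unchanged text in the synopsis, 4.1, 5.5 and 6.4.3 does not support that; the documents show a conflict. A reader might also infer that IRC-based progression-free survival and duration of response will be badly distorted because progressions go unread while later deaths count. The documents do not establish this. SAP Table 1 censors at the last valid scan for undocumented progression and for new anticancer treatment, and a late death could count only if survival follow-up had captured it. Investigator-based versions of both endpoints are planned as well.

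**Conclusion.** The conflict is real and worth correcting. For subjects still on treatment at Amendment 4, the schedule in force and the off-study sentence contradict the sections that keep them in survival follow-up. Literal compliance would give informative and site-dependent censoring of a secondary endpoint that has its own planned analysis.

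The effect is limited. The total cannot be sized without the number still on treatment. The late part of the OS curve is mainly at risk, and the planned median may not move. The primary response rate is unaffected, because it is analysed once every subject has had at least one postbaseline assessment or has progressed, withdrawn or died.

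The consequence assumes that at least some sites follow the Amendment 4 text as written and that the hazard of death is higher after progression. The IRC point is a secondary clarification: the texts disagree, and no numerical effect is claimed.

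**What to change.** - In 7.5.1 and 7.5.2, replace the off-study wording with: *taken off study treatment and entered into survival follow-up (Section 6.4.3)*.
- Add a line to Table 6: *survival status and new anticancer therapy, every 12 weeks, by phone or email*, as Table 4 footnote f already allows.
- As a secondary clarification, state in 7.5.4 whether scans after Amendment 4 still go to the IRC, and bring SAP 7.2.1 into line.

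The cost is a clarification letter or short protocol amendment and a few phone or email contacts per remaining subject, which Table 4 already provided for. The OS analysis needs no SAP change. A short SAP amendment is needed only if IRC submission stops.
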